PCT will be documented by appropriate laboratory measurements carried out in the Porphyria Laboratory at UTMB or another reliable clinical laboratory. This can be done before or after enrollment in an outpatient clinic or at an initial visit to a Clinical Research Center (CRC). Participants are considered to be enrolled after they complete the informed consent process, and will be assigned a Patient Number. Subjects found to be not eligible after enrollment will be recorded as screening failures to be replaced. A recruit to replace approach will be utilized to achieve final recruitment goals. A relapse during follow up can be treated within the study, but will not be part of the primary analysis.

Table 1. Inclusion and exclusion criteria for initial and continued enrollment in the study. Inclusion Criteria:

- 1. Willing to give informed consent
- 2. Willing to return to clinic at time points deemed appropriate by the investigator or work with a local physician to have necessary labs done and samples sent to study site
- 3. Age 18 or greater
- 4. Women of child-bearing potential must be willing to avoid pregnancy and use an accepted and effective contraceptive method during treatment.
- 5. Well-documented PCT:
 - Clinical features- A history of blistering cutaneous photosensitivity and/or skin fragility. Subjects with subclinical PCT who have diagnostic porphyrin elevation but do not have symptoms may also be included.
 - ii.Biochemical and molecular findings a and b are required
 - a. A substantial increase in urinary porphyrins [>450 nmol/24 hours or g of creatinine, or more than 1.5-fold increase (relative to ULN of 300 nmol/24 hours or g of creatinine *or* >300 ug/24 hours or g of creatinine, or more than 1.5-fold increase (relative to ULN of 200 ug/24 hours or g of creatinine)] and/or plasma porphyrins [>2.7 ug/dL, or >3-fold increase (relative to ULN of 0.9 ug/dL), and a fluorescence peak at ~619 nm], with a predominance of uroporphyrin and heptacarboxylateporphyrin in urine or plasma, and normal or only slightly elevated urine ALA and normal PBG.
 - b. Normal or only slightly elevated erythrocyte porphyrins [<200 ug/dL, or less than 1.5-fold increase (relative to ULN of 80 ug/dL)], unless elevated erythrocyte protoporphyrin are due to a non-porphyric condition in the opinion of the investigator. This is to exclude mild cases of CEP and HEP, which may have urine findings similar to PCT.

iii.

Exclusion Criteria:

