- 1. Evidence for another cause of blistering skin lesions, such as another type of cutaneous porphyria, or pseudoporphyria
- 2. Pregnancy
- 3. Prior treatment by phlebotomy, hydroxychloroquine or chloroquine within one month, unless all appropriate lab results from before treatment was started can be obtained, to document baseline porphyrin levels.
- 4. Unwillingness to comply with the protocol and required visits
- 5. Previous treatment as a participant in this protocol.

Pregnant women will not be included in the study, because it is generally recommended that treatment of PCT be delayed in pregnant women until 1-2 months after delivery. Phlebotomies may induce borderline iron status during pregnancy, which may compromise fetal health. Usage of 4-aminoquinoline compounds during pregnancy should be avoided because these drugs cross the placenta and accumulate in ocular tissues of the fetus.

In very rare instances a subject that is an excellent candidate for the study may not meet all inclusion/exclusion criteria. If the investigator feels the subject may still be a good candidate for the study, entrance to the study will be reviewed with the Study Chair and the site's IRB to determine participation. Reasons for the exception must be recorded on the CRF. The objective is to include in the study all patients who need to be treated and obtain information and experience to better define future treatment guidelines.

Documentation of PCT will include consistent cutaneous symptoms and signs, increases in urinary total porphyrins with a predominance of highly carboxylated porphyrins (uroporphyrin, hepta-, hexa- and pentacarboxylate porphyrin) and increased plasma total porphyrin with a plasma fluorescence emission spectrum at neutral pH at 619~620, which is consistent with PCT. Participants with subclinical PCT (i.e. without skin manifestations) and biochemical documentation can also be included. Additional testing will exclude other blistering cutaneous porphyrias such as variegate porphyria, and erythrocyte total porphyrin measurement will exclude congenital erythropoietic porphyria, which rarely mimics PCT. Samples required for these tests prior to treatment include a 24 hour urine collection or a spot urine sample, a blood sample; a random fecal sample is optional but recommended. Testing and laboratory methods will include the following:

- Plasma total porphyrins (25, 26, 64)
- Urinary δ-aminolevulinic acid and porphobilinogen (73)

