4.I. Follow Up Phase. Determining durability of treatment after achieving a complete biochemical remission of PCT is an important objective of this study. Therefore, subjects will be observed long term during the Follow Up Phase for clinical and biochemical recurrences of PCT. This phase will begin after treatment is completed and all treatment outcomes are achieved. These visits will occur, either on site or remotely, every 3-6 months for up to 5 years, or possibly longer, depending on the availability of funding for the study. Symptoms will be monitored, and porphyrin levels measured for early detection of recurrence. Determinations on these visits will include total plasma and urinary porphyrin concentrations, plasma porphyrin neutral pH fluorescence emission peak, urinary porphyrin HPLC, ferritin and liver function tests. These samples may be obtained at the study site or elsewhere as part of standard of care. This will provide information on both clinical and subclinical biochemical recurrence after remission with both types of treatment. If a subject has a recurrence of symptoms their treatment will be followed clinically and they will continue with this follow up visit schedule.

It is important to assess both symptoms and porphyrin levels during follow up. In our experience patient reports of recurrence of skin manifestations are not always reliable, and can be discounted if evaluation at the time finds that porphyrin levels remain normal and no objective skin changes consistent with PCT are present. Conversely, biochemical recurrence with small or large increases in porphyrins can occur in the absence of symptoms. It is suspected that subclinical PCT may be especially common in patients with *UROD* mutations, but this is not well documented.

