- **4.J. Study duration and end of study.** The duration of the study including the Follow Up Phase is at least five years. It is possible that the study will be extended further depending on results and the availability of funding. Subjects will enter the study needing treatment, and require up to 24 months of treatment and observation to document achieving the treatment outcomes, followed by at least 3 years of follow-up. Therefore, the most frequent study visits will occur during the Treatment Phase and generally the first ~12 months of the study, which includes active treatment and the treatment outcome windows to document biochemical remission. Based on the interim analysis (45) it is anticipated that the first outcome (a normal plasma porphyrin concentration) will be reached within 6-7 months, on average. Other treatment outcomes should be achieved within ~12 months, although this is uncertain at present, since such observations were not part of the interim analysis.
- **4.K. Treatment outcomes and schedule of events.** A schedule of events in tabular form and a study flow diagram are shown below. This study compares time to reaching certain efficacy outcomes with the two treatments and documents durability of treatment in terms of absence of increases in porphyrins and recurrence of symptoms.

The primary efficacy outcome is achieving a normal plasma porphyrin concentration (<0.9 mcg/mL). Secondary efficacy outcomes include achieving (1) absence of a fluorescence peak in diluted plasma at neutral pH; (2) a normal level of total urinary porphyrins; (3) a normal pattern of individual porphyrins in urine (defined as total highly carboxylated porphyrins less than coproporphyrin); (4) times to achieving intermediate improvements in these porphyrin

measures, which will be defined during data analysis; (5) absence of new skin lesions for at least 3 months; and (6) effects of susceptibility factors such as hepatitis C, inherited UROD deficiency, etc. on achieving these treatment outcomes.

Durability of treatment (i.e. absence of recurrence) is recorded as beginning with the time that treatment achieves the treatment outcomes, and extends to the time of repeat documentation of a normal plasma porphyrin concentration, assuming there have been no interim recurrences of skin manifestations.

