A total of at least 100 participants will be assigned, based on medical criteria, preference, or (if eligible for both treatments) by randomization, to one of these standard treatment groups. CRFs will be completed for each patient, including porphyrin levels, and data entered into the study database. This database is designed by and housed at the Data Management and Coordinating Center (DMCC) at the University of South Florida in Tampa. The DMCC is supported by the NIH Rare Diseases Clinical Research Network and serves as the secure repository for de-identified data for all consortia in the Network. Upon approval from the UTMB IRB and the Porphyrias Consortium DSMB, data from patients previously enrolled in this study at UTMB starting in 2006 before the study was a RDCRN study will be entered into the database. Subjects will be contacted to give their consent for this data transfer to the DMCC and storage in a federal data repository. For subjects who are now deceased consent will be obtained from next of kin. For subjects who cannot be re-contacted or where the next of kin cannot be re-contacted, approval of the UTMB IRB and the Porphyrias Consortium DSMB will be sought for this data transfer. Transferring this previously collected de-identified data is not expected to cause any increased risks to subjects. Data will be verified and edited where necessary for completeness and consistency by comparison with source documents. Study outcomes, such as time to achieving biochemical endpoints, will be determined from this data. As was found in the interim analysis, assignment to the two groups is unlikely to be equal, and more will be assigned to phlebotomy than to hydroxychloroquine. As in the interim analysis, times to achieving measures of remission are not expected to be substantially different for the two treatment groups. Effects of multiple susceptibility factors and other clinical and demographic features on treatment response and durability will be further examined. Outcome measures such as time to remission will be compared using Cox proportional models to study the effects of susceptibility factors on the hazard ratio to compare the two treatments. All patients who start treatment will be included in the analysis. Safety measures will be compared more descriptively where the adverse effects of each type of treatment are different.

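### The skin-lesion secondary outcome has no baseline-lesion condition, so participants admitted without skin disease will usually count as responders, and group comparisons can be biased if such entrants are unevenly spread

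*Combined protocol and SAP*

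**What the plan says.** - **Outcome.** 4.K, secondary efficacy outcome (5), is "absence of new skin lesions for at least 3 months". No lesion at entry is required, no start of the 3-month period is given, and no analysis set is named for it.
- **Entry.** Table 1 (4.E) sets the clinical criterion as "A history of blistering cutaneous photosensitivity and/or skin fragility" and then adds: "Subjects with subclinical PCT who have diagnostic porphyrin elevation but do not have symptoms may also be included". The text after Table 1 repeats the allowance: "Participants with subclinical PCT (i.e. without skin manifestations) and biochemical documentation can also be included". The synopsis gives the clinical criterion without it.
- **Analysis set.** 4.R: "All patients who start treatment will be included in the analysis". No exception is made for the skin outcome.
- **Susceptibility factors.** 4.K item (6) looks at "effects of susceptibility factors such as hepatitis C, inherited UROD deficiency, etc. on achieving these treatment outcomes", and it follows the skin outcome in the same list. 4.E names UROD mutations as one of three factors of most clinical interest, with an estimated prevalence of 20%.
- **Subclinical disease and UROD.** 4.I: "It is suspected that subclinical PCT may be especially common in patients with" UROD mutations. The same sentence adds that this is not well documented.
- **Existing safeguard.** Section 4 (opening text) and 4.G count an outcome only when an abnormal result is followed by a normal one within a window. Table 5 applies this to four porphyrin measures and does not list skin lesions.

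**The concern.** An outcome defined as the absence of something measures response only in people who had it to begin with. A participant who enters with clear skin and stays clear for three months satisfies outcome (5) without any change having occurred. This has two consequences.

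- **Level.** The reported skin response is too high in any group that contains lesion-free entrants.
- **Comparison.** If lesion-free entrants are more frequent in one group, that group appears to respond more often or faster. Randomization would guard against this between treatments, but 4.B expects most participants to be assigned by medical indication and preference. UROD status is not randomized at all.

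The outcome is not incidental. 4.B makes time to remission a main objective, assessed by primary and secondary biochemical and clinical outcomes, and outcome (5) is the clinical one among the 4.K efficacy outcomes.

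**Working it through.** **1. Figures in the plan.** The plan states no sample size, power or response rate for the skin outcome, so there is nothing to reproduce. The power statement in 4.R concerns time to remission.

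**2. Inputs.** From the documents: total 100 (synopsis); UROD prevalence 20% (4.E), so about 20 carriers and 80 non-carriers; a Cox model for time-to-outcome comparisons (4.R); up to 24 months to reach outcomes (4.J). Assumed, because the documents are silent: the lesion-free share *s*, the true response *p* among those with lesions, and the distribution of time to the last new lesion.

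**3. Level of response.** If lesion-free entrants all count as achieving the outcome, the reported share is *s* + (1 − *s*)*p*, an inflation of *s*(1 − *p*). With *s* = 0.10:

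- *p* = 0.5: 0.10 + 0.90 × 0.5 = 0.55
- *p* = 0.7: 0.10 + 0.90 × 0.7 = 0.73
- *p* = 0.9: 0.10 + 0.90 × 0.9 = 0.91

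**4. Group comparison as a proportion.** Take *p* = 0.7 in both groups, with 30% of carriers and 5% of non-carriers lesion-free. Carriers: 0.30 + 0.70 × 0.7 = 0.79. Non-carriers: 0.05 + 0.95 × 0.7 = 0.715. Apparent odds ratio: (0.79/0.21)/(0.715/0.285) = 1.50, where the truth is 1. The same arithmetic applies to the two treatment groups.

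**5. Group comparison as time to outcome.** Two Cox simulations were run with a true UROD hazard ratio of 1 and lesion-free entrants credited at month 3.

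- Setting A: 90 participants (18 carriers), others at 3 months plus a gamma time (shape 2.5, scale 2.0), 800 trials.
- Setting B: 20 carriers and 80 non-carriers, others at 3 months plus an exponential time with median 6.5 months (borrowed from the 6–7 months in 4.J for plasma porphyrin), censored at 24 months, 300 trials.

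| Lesion-free share, carriers / non-carriers | HR, A | False positives, A | HR, B | False positives, B |
|---|---|---|---|---|
| 10% / 10% | 1.01 | 5% | 1.03 | 9% |
| 10% / 5% | 1.09 | 8% | – | – |
| 10% / 0% | – | – | 1.13 | 11% |
| 20% / 5% | 1.21 | 15% | 1.23 | 13% |
| 30% / 5% | 1.37 | 24% | 1.42 | 30% |
| 40% / 10% | 1.52 | 34% | 1.50 | 34% |

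The 9% in setting B at equal shares is simulation noise. With equal shares the two groups have the same distribution, so the error rate should be near nominal, and a rerun of setting B with 10,000 trials gave a hazard ratio of 1.01 and 5.1%. The same length of run gave 14–15%, 26–29% and 35–38% for the last three rows across the two settings, so the table is adequate to within a few points.

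**6. After restriction.** Restricting setting B to participants with lesions at entry gave hazard ratios of 1.00–1.04 and false-positive rates of 3–7% in every scenario.

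**The case against.** Several points can be made for the plan, and some of them limit the finding.

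- **UROD bias.** A reader might infer that the UROD comparison is biased as a matter of fact. The documents do not support that. The link between UROD mutations and subclinical disease in 4.I is a suspicion that the protocol itself calls not well documented. It appears in the follow-up section, after a remark on recurrence without symptoms, and says nothing of who is lesion-free at entry. At equal shares there is essentially no bias.
- **Automatic success.** A reader might infer that lesion-free entrants meet the outcome whatever treatment does. That is too strong: 5.A and 5.H.3 expect transient worsening of photosensitivity on low-dose hydroxychloroquine, so a lesion-free entrant could develop lesions. In such a person, however, outcome (5) measures freedom from new harm and not remission, which argues for separate reporting.
- **History only.** A reader might infer from Table 1 that old, quiescent disease is routinely enough for entry. The 4.E text says documentation of PCT will include consistent cutaneous symptoms and signs, with subclinical disease as the exception. The explicit subclinical allowance is the secure basis for the point.
- **Scope of the analysis.** 4.G describes the treatment outcomes as times to normalization of porphyrin measurements, and 4.M says efficacy is judged mainly on laboratory results. A Cox analysis of skin response by UROD status is therefore a natural reading of 4.K and 4.R, but not an explicit instruction.
- **Consequence.** 4.R calls the approach descriptive and concedes that susceptibility subgroups may be small. That bears on precision; it does not remove a systematic error in what is counted.

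**Conclusion.** The definitional gap stands. As written, outcome (5) has no baseline-lesion condition, participants without skin manifestations may enter, and all who start treatment are analysed. Applying the outcome to everyone follows from the absence of any restriction together with the 4.R analysis set.

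The inflation of the response rate needs only that some lesion-free participants enrol and that not everyone with lesions responds: 3 percentage points at a 10% share and 70% true response, with both figures assumed. Bias in the treatment or UROD comparison is conditional on unequal lesion-free shares. It ranges from none at equal shares to an apparent hazard ratio of about 1.5, with about a one-in-three false-positive rate, at 40% against 10%. No share in that range comes from the documents.

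The effect is confined to one secondary outcome. The primary plasma porphyrin outcome and the other porphyrin outcomes are untouched. The change is worth making but does not threaten the main result.

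**What to change.** 1. In 4.K and 4.R, extend the existing abnormal-then-normal principle to outcome (5): analyse it only in participants with active or new lesions documented at the baseline PCT Symptom Assessment or examination. A 3-month look-back before entry is less suitable, because the baseline window is Day −60 to Day −1 and is not stated to capture three months of lesion history.
2. State that the 3-month lesion-free period starts after the last documented new lesion.
3. Report lesion-free entrants separately by treatment group and UROD status, including any new lesions that appear on treatment. This keeps any treatment-related worsening visible and gives data on the suspicion voiced in 4.I.
4. Reconcile the synopsis clinical criterion with Table 1 and the 4.E text on subclinical disease.

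The data are already planned: symptoms are assessed at baseline (Schedule of Events) and new lesions are counted at each visit (4.M). The cost is one derived baseline flag, a few sentences of analysis text, and a smaller denominator for this one secondary outcome.

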4.C. Treatment definitions. For participants assigned to Group 1, the treatment regimen will be hydroxychloroquine 100 mg twice weekly until at least one month after plasma porphyrin levels are normal and other biochemical outcomes (absence of a plasma fluorescence peak at ~619 nm, a normal total urinary porphyrin level and a normal pattern of individual urinary porphyrins by HPLC) are achieved, with a maximum of 24 months of treatment.

Hydroxychloroquine is available only as 200 mg unscored tablets. Participants in Group 1 will be supplied with half tablets containing hydroxychloroquine 100 mg and instructed to take one half tablet twice weekly, and on a specific schedule, such as every Monday and Thursday, or Tuesdays and Friday. Participants will be supplied with tablets that have been halved with a razor blade by the Pharmacy at UTMB and supplied to each of the study sites. The FDA CDER has suggested that with regard to the proposed strength of the half tablet, we follow the procedures outlined for the physical test for the "Uniformity of Dosage Limits" found in the USP, as follows:

- Weigh and record the weight of each whole tablet
- Split the tablet and reweigh each tablet half and record those weights
- Follow the USP physical test for Uniformity of Dosage Units, such that each tablet half should be within a range of 85-115% of the intended 100 mg

This procedure will better assure uniformity of the half tablets used in this study. The UTMB Investigational Drug Pharmacy will supply half tablets to be dispensed to patients at the other sites.

For Group 2, treatment by phlebotomy will consist of removal of one unit (450 ml) of whole blood at intervals of ~2 weeks or as tolerated until a target serum ferritin concentration of ≤20 ng/ml is reached. A serum ferritin of ≤25 ng/ml on the same day as the last phlebotomy will also be regarded as a satisfactory target ferritin concentration. The time to achieving this target ferritin level will depend on the initial ferritin level and the participant's compliance with the scheduled treatment visits. Suitable sites for phlebotomies may include 1) an outpatient clinic, 2) a blood bank that performs therapeutic phlebotomies or 3) a clinical research center. The phlebotomy site must provide documentation of the procedure to the site investigator. A site that can obtain a sample for a serum ferritin concentration is most desirable.

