During the course of treatment by phlebotomy, samples for measuring serum ferritin and plasma total porphyrins will be obtained at baseline and at intervals of 2 weeks, or as needed to document achieving the target serum ferritin of \leq 20 ng/mL. Documenting a serum ferritin of \leq 25 ng/mL on the same day as the last phlebotomy will satisfy this requirement. Ferritin levels may not be needed every 2 weeks early in the course of treatment, but should be measured most frequently (biweekly) once the ferritin falls below 60 ng/mL and is approaching the target value of \leq 20 ng/mL.

Samples for tests such as blood counts and serum chemistries will be obtained at baseline, during the treatment phase of the study only when clinically indicated, during the post treatment phase when clinically indicated, and at the end of the follow up phase. This is the standard approach to the treatment of PCT by repeated phlebotomy in the U.S. and other countries.

It is best if therapeutic phlebotomies can be done at a site that can also send blood samples for ferritin, plasma porphyrins, blood counts and chemistries and urine porphyrins, when needed. Otherwise, additional visits will need to be arranged for monitoring these test results.

Phlebotomies will be discontinued once the target serum ferritin (\leq 20 ng/mL) is reached, which is before porphyrin levels and patterns normalize. The ferritin level should be repeated 2 weeks after the last phlebotomy, unless a ferritin of \leq 25 ng/mL was documented on the same day as the last phlebotomy. Porphyrin levels will continue to be monitored after phlebotomies have been discontinued in order to document times to each treatment outcome.

Most facilities that do phlebotomies require that a consult request or orders be provided. Suggested wording for such requests is as follows, which will need to be modified for each site and permitted hematocrit (or hemoglobin) values specified for each participant:

Please start repeated phlebotomies at intervals of approximately 2 weeks for treatment of porphyria cutanea tarda (PCT). The treatment target is a serum ferritin from the previous visit of less than 25 ng/mL.

- 1. Please call the patient to schedule the first visit.
- 2. At each visit, please
 - a. obtain an hematocrit
 - b. send a blood sample to Clinical Chemistry for serum ferritin and
 - c. obtain a blood sample for total plasma porphyrins (green top tube call extension xxxx for pickup).

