The treatment outcomes for this study are documentation of times to normalization of several porphyrin laboratory measurements, which occur in sequence at different times during the Treatment Phase. Study performance will be assessed by whether or not primary study outcomes are documented within specified time windows. *Documenting the time to each outcome requires an abnormal result followed by a normal result within a specified time window.* The windows of documentation for each treatment outcome are shown in Table 5. Experience to date indicates that these outcomes are usually achieved in the order shown. All outcome measures may not be documented in all patients, but with four rather than one outcome measure it is more likely that each patient will achieve documentation of at least some of these outcomes.

| Table 5. Treatment outcomes and windows for documentation | | |
|---|------------------|--|
| Treatment Outcomes | Windows for | |
| | Documentation of | |
| | Outcomes | |
| Normal plasma porphyrin level | 4 weeks | |
| Disappearance of plasma fluorescence peak | 8 weeks | |
| at ~619 nm | | |
| Normal urine total porphyrins | 8 weeks | |
| Normal pattern of urinary porphyrins | 8 weeks | |

Time to achieving each of these treatment outcomes and the location of each of these outcome windows in time during the Treatment Phase will vary among individual participants. For this reason, regular visits should be scheduled based on these windows, and less frequent visits scheduled only after examination of the most recent laboratory results.

4.H. End of treatment. The maximum duration of treatment will be 24 months, but is expected to be shorter for most participants. Treatment by phlebotomy will end when the target ferritin value is reached (≤20 ng/mL, or ≤25 ng/mL on the day of the last phlebotomy). Therefore, it is advantageous, if possible, to obtain ferritin measurements on the days of phlebotomy. Porphyrin levels will start to decrease, but will not be normal when phlebotomies are ended. Therefore the Treatment Phase of the study extends beyond the last phlebotomy until all treatment outcomes are documented. Factors that may lengthen the duration of phlebotomy treatment include marked iron overload, some loss of venous access and difficulty adhering to treatment visits.

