Hydroxychloroquine treatment will end after the plasma total porphyrin concentration and other porphyrin abnormalities have been normal for at least one month (i.e. at least one month after all treatment outcomes are achieved). Treatment may be stopped for poor tolerance or other medical reasons, and these reasons will be recorded. For hydroxychloroquine, the desirable length of this treatment and factors that delay response are less well understood, and will be clarified by the results of this study. For this protocol, the duration of hydroxychloroquine treatment will not exceed 24 months.

Either treatment will be discontinued if a participant no longer meets the inclusion criteria or develops one of the exclusion criteria for the assigned treatment. A treatment will also be stopped if an adverse event occurs that is regarded as a reason for stopping the current

treatment or in the judgment of the investigators on clinical grounds is a reason for stopping the current treatment in the best interest of the patient. The reasons for discontinuing treatment will be recorded on the CRFs. If a participant is discontinued from one treatment, they may be switched to the alternate treatment if deemed appropriate by the investigator. Should this happen their information will still be collected according to the schedule described in this protocol and analyzed as part of this study.

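### Section 4.K starts the durability clock while hydroxychloroquine is in general still being taken, whereas 4.I starts recurrence follow-up only after treatment ends

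*Combined protocol and SAP*

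**What the plan says.** Four sections set the relevant dates.

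- **Start of durability (4.K).** "Durability of treatment (i.e. absence of recurrence) is recorded as beginning with the time that treatment achieves the treatment outcomes". The rule is the same for both arms. Table 5 in 4.G lists four treatment outcomes: normal plasma porphyrin, loss of the plasma fluorescence peak, normal urine total porphyrins and a normal urine pattern.
- **End of hydroxychloroquine (4.C, 4.H).** Section 4.C runs dosing "until at least one month after plasma porphyrin levels are normal and other biochemical outcomes" are achieved. Section 4.H puts the end of dosing "at least one month after all treatment outcomes are achieved". The only upper limit is that "the duration of hydroxychloroquine treatment will not exceed 24 months".
- **End of phlebotomy (4.F, 4.H).** Section 4.F stops phlebotomies once the ferritin target "is reached, which is before porphyrin levels and patterns normalize". Section 4.H agrees: "Porphyrin levels will start to decrease, but will not be normal when phlebotomies are ended".
- **Start of recurrence follow-up (4.I).** "This phase will begin after treatment is completed and all treatment outcomes are achieved".

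Section 4.B makes durability after each treatment a main objective. Secondary objective 2 in the synopsis compares recurrence after treatment with each method. The hypothesis in 1.B is that durability is comparable. Section 4.R plans logistic regression for the frequency of recurrence and names no time origin or observation window.

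**The concern.** Under 4.K a hydroxychloroquine participant who follows the general rule is still taking the drug at time zero and for at least the first month of the durability interval. A phlebotomy participant at the same point has finished treatment. If the drug suppresses porphyrins while it is taken, that month cannot show durability after treatment, yet 4.K records it as such in one arm only. The error lengthens apparent recurrence-free time on hydroxychloroquine and so leans towards the stated hypothesis.

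Section 4.I does not have this problem because it also requires treatment to be complete. For phlebotomy, 4.I and 4.K give the same date. For hydroxychloroquine they differ by a month or more, and no section reconciles them. Two analysts could derive different durability times from the same data.

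**Working it through.** The protocol gives no recurrence rate and no effect size or power for durability, so it has no figure to reproduce. The check compares dates first and then illustrates size under stated assumptions.

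**1. Dates side by side, under the general rule**

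| | Hydroxychloroquine | Phlebotomy |
|---|---|---|
| Last treatment | at least 1 month after all outcomes (4.C, 4.H) | before porphyrins are normal (4.F, 4.H) |
| 4.K time zero | date outcomes achieved | date outcomes achieved |
| 4.I time zero | end of treatment | date outcomes achieved |
| On-treatment time after 4.K time zero | at least 1 month | 0 |

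Section 2 puts the ferritin target at 3-4 months and remission at 6-7 months. Phlebotomy participants are therefore about 6 - 4 = 2 to 7 - 3 = 4 months past their last phlebotomy when remission is reached.

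**2. Observed recurrence at 36 months** (4.J gives at least 3 years of follow-up)

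Assumptions: a constant hazard off drug giving 20% recurrence at 36 months, zero hazard on drug, and d on-drug months after the 4.K date.

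- λ = -ln(0.8)/36 = 0.0062 per month.
- Observed recurrence = 1 - exp(-λ(36 - d)).
- d = 0: 20.0%. d = 1: 19.5%. d = 3: 18.5%.

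The one-month overlap is the minimum in the text. Three months is an assumption for illustration.

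**3. Apparent rate ratio when true durability is equal**

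For follow-up of F months from the 4.K date, let p = 1 - exp(-λ(F - d)). Hydroxychloroquine contributes p events over d + p/λ months per participant. Phlebotomy has event rate λ. The ratio is p/(λd + p).

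Example with an assumed 10% annual recurrence: λ = -ln(0.9)/12 = 0.00878. With F = 36 and d = 1, p = 0.2646 and the ratio is 0.2646/(0.0088 + 0.2646) = 0.968.

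Ranges over assumed annual recurrence of 5% to 20%:

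| Overlap | F = 12 | F = 36 | F = 60 |
|---|---|---|---|
| 1 month | 0.909-0.915 | 0.963-0.970 | 0.973-0.981 |
| 3 months | 0.734-0.746 | 0.892-0.911 | 0.921-0.944 |

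One month is 8.3% of a 12-month window, 2.8% of 36 months and 1.7% of 60 months. If time zero is the later of outcomes achieved and last treatment, the on-drug credit is 0 and the ratio is 1.00.

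**The case against.** The strongest reply is that the recurrence plan largely sidesteps the problem. Section 4.F follows patients for recurrence after treatment is completed, 4.I places that observation in the Follow Up Phase, and 4.R models frequency of recurrence by logistic regression. No section specifies a time-to-recurrence comparison from the 4.K date. If recurrence is counted yes/no within the Follow Up Phase, on-drug time earns hydroxychloroquine no credit. This stands as a limit on the consequence. It does not remove the conflict, because 4.K says how durability is recorded and 4.R names no window.

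The second reply is about size, and it also stands. At the one-month minimum the shift is 0.5 points. With about 50 per group (4.R), the standard error of a difference near 20% is √(2 × 0.2 × 0.8/50) = 0.08, or 8 points. Follow-up visits 3-6 months apart date a recurrence more coarsely than one month.

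Third, moving time zero does not equalise the arms. Phlebotomy participants would still be further from their last treatment. Setting aside on-drug rises in one arm, while the same early rise after phlebotomy counts as recurrence, would create a new asymmetry favouring hydroxychloroquine. This stands and shapes the fix.

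Fourth, 4.K ends the interval at a repeat normal plasma porphyrin, not at a recurrence, so correcting the start alone does not yield a time to recurrence. That is a separate gap in the same sentence.

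**Conclusion.** The conflict between 4.K and 4.I is in the text. As written, 4.K in general counts at least one on-drug month as durable remission for hydroxychloroquine and none for phlebotomy, on an objective defined as durability after treatment. The direction favours hydroxychloroquine. The size is small at the minimum overlap: 20% becomes 19.5% at 36 months, or 18.5% with three months, assuming a constant off-drug hazard and no recurrence on drug. It applies when durability is measured as a duration or rate from the 4.K date.

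Three stronger readings are not supported:

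- A reader might infer that every hydroxychloroquine participant is on drug at time zero. Section 4.H allows stopping for intolerance and caps treatment at 24 months, so some will have no overlap.
- A reader might infer an overlap of up to 24 - 12 = 12 months, or that phlebotomy participants are 12 - 4 = 8 months off treatment at time zero. Both use the ~12-month outcome timing that 4.J calls uncertain. The first also assumes that responders are dosed to the cap, which nothing in 4.H suggests.
- A reader might infer that the recurrence comparison is certainly biased. A yes/no count within the Follow Up Phase would largely avoid this.

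The correction is worth making because it is cheap and the error runs one way.

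**What to change.** Reconcile 4.K with 4.I through a single time zero for durability in both arms: the later of (a) the date the last treatment outcome is documented and (b) the date of the last hydroxychloroquine dose or last phlebotomy. For phlebotomy this is in general date (a), so nothing moves. Name the same origin in 4.R for the recurrence analysis.

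Report porphyrin rises between (a) and (b) separately. Add a supporting analysis from date (a) in both arms that counts those rises as recurrences, so that excluding them does not favour hydroxychloroquine. Read the two results together.

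This is an analysis definition and implies no change to dosing. The dates should be derivable from the dosing diaries and phlebotomy reports already required in 4.F. The cost is slightly shorter hydroxychloroquine follow-up and one extra analysis.
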